5.2.2.1.2. Unsolicited Adverse Events

For analysis of unsolicited AEs, SAEs, pIMDs and concomitant medications, all vaccinated participants will be considered. Participants who did not report an event or concomitant medication will be considered as participants without the event or the concomitant medication, respectively.

When an unsolicited adverse event occurs more than once for a participant, the maximal severity and strongest relationship to the vaccine group will be counted. The selection of unsolicited AEs reported during the follow-up period will be done using the day of onset.

Listing of AEs/SAEs leading premature withdrawal from study or to interruption of vaccination will be described in detail.

5.2.2.1.3. Combined Solicited and Unsolicited Adverse Events

A summary of participants with all combined solicited (regardless of their duration) and unsolicited adverse events will be provided. Solicited events will be coded by MedDRA as per the following codes

Solicited symptom	Lower level term code	Corresponding Lower level term decode
Pain	10022086	Injection site pain
Erythema	10015150	Erythema
Swelling	10053425	Injection site swelling
Fever	10016558	Pyrexia

For clinicaltrials.gov and EudraCT posting purposes, a summary of combined solicited and unsolicited non-serious adverse events will be produced by System Organ Class and preferred terms and according to occurrence of each event.

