10.3.3. Solicited events**a. Solicited administration site events**

The following administration site events will be solicited:

Table 14 Solicited administration site events

Pain at the injection site
Erythema at the injection site
Swelling at the injection site

CONFIDENTIAL213569 (RSV OA=ADJ-011 EXT:002 MTH20)
Protocol Amendment 1 Final**b. Solicited systemic events**

The following systemic events will be solicited:

Table 15 Solicited systemic events

Fever

Note: participants will be instructed to measure and record the oral body temperature in the evening. Should additional temperature measurements be performed at other times of day, participants will be instructed to record the highest temperature in the diary card.

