Unsolicited adverse event:	Any AE reported in addition to those solicited during the clinical study. Also, any 'solicited' symptom with onset outside the specified period of follow-up for solicited symptoms will be reported as an unsolicited adverse event.

CONFIDENTIAL213569 (RSV OA=ADJ-011 EXT:002 MTH20)
Protocol Amendment 1 Final**10.5. Appendix 5: Protocol Amendment history**

The Protocol Amendment Summary of Changes Table for the current amendment is located directly before the Table of Contents (TOC).

DOCUMENT HISTORY	
Document	Date of Issue
Original Protocol	2 July 2020

Overall Rationale for the Amendment

The protocol is amended to address the comments from the United States Food and Drug Administration (US FDA). Specifically, instructions to delay enrolment or vaccination of participants with symptoms suggestive of Coronavirus Disease 2019 (COVID-19) infection or with known COVID-19 positive contacts have been updated. In addition, the requirement to obtain written approval from the Sponsor for a participant to receive a vaccine as part of mass vaccination for an unforeseen public health threat (e.g., pandemic) if the vaccine to be used according to the local governmental recommendations has been amended. Other changes have been made to align the protocol with the parent RSV OA=ADJ-002 study and other phase 3 studies in the project.

Detailed description of Protocol Amendment:

Sponsor Approval: The name of the Sponsor Signatory has been updated.

~~[name]~~ **[name] [name].**

Clinical and Epidemiology R&D Project Lead, Older Adults project

Section 5.2.2: Prior/ Concomitant therapy: Updated to acknowledge the FDA's request to remove the requirement to obtain written approval from the Sponsor for mass vaccination.

Note: In case an emergency mass vaccination for an unforeseen public health threat (e.g.: a pandemic) is recommended and/or organized by the public health authorities, outside the routine immunization program, the time period described above can be reduced if necessary for that vaccine provided it is licensed and used according to the local governmental recommendations and provided a written approval of the Sponsor is obtained **that the Sponsor is notified accordingly.**

Section 7.1.1 Criteria for temporary delay for enrolment and/or vaccination:

Updated to acknowledge FDA feedback.

~~Use of antipyretics and/or analgesics and/or antibiotics within 3 days prior to vaccination.~~

CONFIDENTIAL

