5.2. Primary endpoint(s)

5.2.1. Analysis planned in the protocol

5.2.1.1. Safety analysis

The safety analysis will be performed on the ES for all participants.

A descriptive analysis by group and overall will present a summary of:

- The number and percentage of participants with at least one administration site event (solicited and unsolicited), with at least one systemic event (solicited and unsolicited) and with any AE during the 4-day or 30-day follow-up period will be tabulated with exact 95% CI after Dose 3. The same computations will be done for Grade 3 AEs, Grade 3 non-serious AEs, related AEs and AEs resulting in a medically attended visit.
- The number and percentage of participants reporting each individual solicited administration site event (any grade, Grade 3, with medically attended visit) and solicited systemic event (any grade, Grade 3, with medically attended visit) during the 4-day follow-up period (i.e., on the day of vaccination and 3 subsequent days) will be tabulated for each group after Dose 3.
- For fever, the number and percentage of participants reporting fever by half degree ($^{\circ}\text{C}$) cumulative increments during the 4-day follow-up period (i.e., on the day of vaccination and 3 subsequent days) will be tabulated for each group after Dose 3.
- The number and percentage of participants with any unsolicited AEs during the 30-day follow-up period (i.e., on the day of vaccination and 29 subsequent days) with its exact 95% CI will be tabulated by group and by Medical Dictionary for Regulatory Activities (MedDRA) preferred term. The same tabulation will be done for Grade 3 unsolicited AEs, for any causally related unsolicited AEs, for Grade 3 causally related unsolicited AEs and for unsolicited AEs resulting in a medically attended visit. The verbatim reports of unsolicited AEs will be reviewed by a qualified person and the signs and symptoms will be coded according to the MedDRA Dictionary for Adverse Reaction Terminology. Every verbatim term will be matched with the appropriate Preferred Term.
- The number and percentage of participants with at least one report of SAE/pIMD classified by the MedDRA Preferred Terms and reported during the 30-day follow-up period (i.e., on the day of vaccination and 29 subsequent days) will be tabulated with exact 95% CI. The same tabulation will be done for related SAEs/pIMDs. SAEs/pIMDs will also be described in detail.

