5.2.2. Additional considerations

5.2.2.1. Safety analysis

5.2.2.1.1. Solicited Events

Solicited events will be reported daily during the 4-day (from Day 1 to Day 4) follow up period after vaccination, using structured diaries. Missing or non-evaluable measurements will not be replaced. Therefore, the analysis of solicited events will include only vaccinated participants with documented solicited safety data (i.e., paper diary completed).

In order to summarize the data, the maximum intensity of local injection site erythema/swelling (in mm) and fever (in °C) will be categorized as follows:

Grading	Erythema/swelling	Fever
0:	≤ 20 mm	< 38.0°C (100.4°F)
1:	> 20 - ≤ 50 mm	≥ 38.0°C (100.4°F) - ≤ 38.5°C (101.3°F)
2:	> 50 - ≤ 100 mm	> 38.5°C (101.3°F) - ≤ 39.0°C (102.2°F)
3:	> 100 mm	> 39.0°C (102.2°F)

Fever is defined as temperature ≥ 38.0°C / 100.4°F (regardless of the location of measurement). The preferred location for measuring temperature in this study will be the oral cavity. Body temperature will also be summarized by 0.5°C increments as follows: ≥38.0, >38.5, >39.0, >39.5, >40.0 °C.

Each participant’s data will be summarized according to the maximal severity observed during the follow-up period for each event, followed by a summary across participants.

- Compliance in completing solicited events information will be tabulated.
- The number of days with solicited events reported during the 4-day follow-up period will be tabulated for each solicited event, using descriptive statistics (mean, min, Q1, median, Q3, maximum). The same tabulation will be done for Grade 3 solicited events.
- The prevalence of each solicited event (any grade and grade 3) will also be represented graphically per group.

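### The SAP codes solicited injection-site erythema to a MedDRA term without a site, while pain and swelling get injection-site terms

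*SAP*

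**What the plan says.** Protocol section 10.3.3, Table 14, lists three solicited administration-site events, and each is tied to the injection site. The one at issue is "Erythema at the injection site". SAP section 5.2.2.1.1 treats it in the same way: it categorises "the maximum intensity of local injection site erythema/swelling (in mm"), with one set of millimetre cut-offs for both signs.

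SAP section 5.2.2.1.3 then sets the lower-level term under which each solicited event is coded. The three local rows are:

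- "Pain 10022086 Injection site pain"
- "Erythema 10015150 Erythema"
- "Swelling 10053425 Injection site swelling"

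The fourth row is fever, a systemic event. The same section says that, for registry posting, "a summary of combined solicited and unsolicited non-serious adverse events will be produced by System Organ Class and preferred terms".

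**The concern.** The protocol and the SAP's grading text define erythema as a local reaction at the vaccination site, of the same kind as pain and swelling. The coding table keeps the site for those two and drops it for erythema. In a table organised by System Organ Class and preferred term, the code determines the row label. A reader of the posted summary could not tell local erythema caused by the injection from erythema elsewhere on the body, and would see one of the three local reactions labelled differently from the other two. The row is an instruction to be programmed, in a summary meant for public registries, so it is more than loose wording.

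**Working it through.** No arithmetic is needed beyond counting rows, and the plan gives no figure to reproduce. The check sets the definitions beside the coding table and follows the codes into the output.

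**1. Definition against code**

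| Solicited local event (Protocol Table 14) | Site in the definition | Term in the SAP coding table | Site in the term |
|---|---|---|---|
| Pain | yes | Injection site pain (10022086) | yes |
| Erythema | yes | Erythema (10015150) | no |
| Swelling | yes | Injection site swelling (10053425) | yes |

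The site is present in 2 of 3 local events and absent in 1 of 3. With fever included, 1 of the table's 4 rows is affected.

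**2. Is it a slip in one version, or explained elsewhere?** The SAP of 1 December 2020 has the identical row. The document history for SAP Amendment 1 (15 July 2021) lists an added elimination code, the new section 5.5 and an update to section 10.1.2.3.1; the coding table is not among the changes. SAP section 8 records no change to the protocol-defined analysis. No other section gives a reason for coding erythema differently.

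**3. Where the code has effect.** The posting summary puts solicited and unsolicited events in one table by preferred term, which has three consequences.

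- Solicited erythema would appear there without its site.
- It would share a row with any unsolicited erythema coded to the same term. SAP section 10.1.3.7 counts events with the same preferred term that start on the same day as one occurrence. A local reaction and a same-day erythema elsewhere in one participant could therefore merge into one.
- There may be a split by onset day. Under the Protocol glossary (section 10.4.2), a solicited "symptom with onset outside the specified period of follow-up for solicited symptoms will be reported as an unsolicited adverse event". Site erythema that begins after Day 4 is then coded from its verbatim text under the rule in SAP section 5.2.1.1: "Every verbatim term will be matched with the appropriate Preferred Term". If the coder chooses a term that carries the site, the same reaction sits under two terms in one table, depending only on the day it began. This last consequence is conditional on that coding choice.

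**4. Where the code has no effect.** The tables of each individual solicited event (SAP section 5.2.1.1) report erythema under its own heading. Grading (section 5.2.2.1.1) uses the millimetre measurement. The split of unsolicited events into administration-site and systemic (section 10.1.3.7) uses a flag on the case report form. None of these depends on the MedDRA term.

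**5. Size.** Neither document gives an erythema rate, so the number of participants or occurrences affected cannot be calculated.

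**The case against.** The strongest case on the other side accepts the mismatch and disputes its consequence and weight.

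- **The preferred term is not printed.** The table gives lower-level terms, while the summary is by preferred term and System Organ Class. How 10015150 rolls up is not in the documents. This stands as a limit: the absence of a site in the posted row is inferred from the printed decode, and the System Organ Class cannot be stated. The inference is nevertheless a natural one, since the term itself names no site and its two neighbours do.
- **The late-onset split is conditional.** This also stands. It needs a reaction starting after Day 4 and a coder who selects a site-specific term. The finding does not depend on it.
- **The information is available elsewhere.** Solicited events are a primary endpoint with dedicated tables, and SAP section 7.1 marks both the Day 31 and the end-of-study analyses for public posting. This narrows the harm to someone reading the combined summary alone. It does not make that summary's label correct.
- **The administration-site flag could restore the site.** Section 10.1.3.7 uses the flag to separate administration-site from systemic events in combined outputs. Nothing says that it labels rows of the preferred-term table.
- **It may be a deliberate convention.** The documents do not exclude this, but they state no such convention. If there is one, the SAP should record it.

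**Conclusion.** The concern holds, as a minor point. The coding table contradicts the protocol's definition of the event and the SAP's own grading text for 1 of the 3 solicited administration-site events. The only preferred-term output shown to use these codes is the registry posting summary, and the effect there is on labelling, pooling and possibly the count of occurrences. No denominator, grade, analysis set or dedicated solicited-event table changes, and the study is descriptive throughout. The mismatch itself can be read directly from the documents and rests on no assumption. That the posted row lacks a site assumes the preferred term follows the printed decode.

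**What to change.** In SAP section 5.2.2.1.3, replace the erythema row with the MedDRA lower-level term for injection-site erythema. Confirm the code and its preferred term in the MedDRA version used for the study, and make the change before the combined and disclosure tables are run. If the non-site term is intended, add a sentence giving the reason and a footnote to the posting summary stating that the row includes solicited injection-site erythema. The cost is one table row, or a sentence and a footnote. No new data are needed and the dedicated solicited-event analyses do not change.

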5.2.2.1.4. Concomitant Medication

Medications will be coded using the GSKDRUG dictionary.

5.2.2.2. Humoral immune response up to 1 month post-Dose 3

- The kinetics of GMTs/GMCs will be plotted as a function of time for participants with results available at all time points, considering also the results from study RSV OA=ADJ-002 study.

5.3. Secondary endpoint(s)**5.3.1. Analysis planned in the protocol****5.3.1.1. Humoral immune response up to 1 month post-Dose 3**

See sections [5.2.1.2](#) and [5.2.2.2](#)

5.3.1.2. CMI response up to 1 month post-Dose 3

The following parameters will be summarized by group using descriptive statistics (N, geometric mean, min, Q1, median, Q3, max) at each time point for which blood samples are collected for CMI:

- Frequency of RSVPreF3-specific CD4+ T-cells identified as expressing at least 2 activation markers among IL-2, CD40L, TNF- α , IFN- γ .
- Fold increase of the frequency of RSVPreF3-specific CD4+ T-cells identified as expressing at least 2 activation markers among IL-2, CD40L, TNF- α , IFN- γ , at each post-vaccination time point over pre-vaccination.

- Distribution of the fold increase: the percentage of participants with at least a 2-fold, 4-fold, 6-fold, 8-fold, 10-fold increase post-vaccination as compared to pre-vaccination (Post over Pre) will be tabulated by timepoint and by group.

The immunogenicity analysis will also be performed by age category (60-69 years and 70-80 years, age according to the parent study).

5.3.1.3. SAEs and pIMDs up to 6 months post-Dose 3

- The number and percentage of participants with at least one report of SAE classified by the MedDRA Preferred Terms and reported during the entire study period will be tabulated with exact 95% CI. The same tabulation will be done for causally related and fatal SAEs. SAEs will also be described in detail.
- The number and percentage of participants with at least one pIMD classified by the MedDRA Preferred Terms and reported during the entire study period will be tabulated with exact 95% CI. The same tabulation will be done for causally related pIMDs. pIMDs will also be described in detail.

5.3.2. Additional considerations

5.3.2.1. CMI response up to 1 month post-Dose 3

Descriptive statistics of the cell-mediated immune response will be tabulated by timepoint and displayed graphically using boxplots (min, Q1, median, Q3, max).

The RSVPreF3-specific CD4+ T cell frequencies will be obtained by subtracting the background value to the antigen-induced value, and by setting to 1 all values less than or equal to zero for geomean calculation and graphical representation. Frequencies will be expressed as the number of cells per million of CD4+ T cells.

More specifically, the frequencies of RSVPreF3-specific CD4+ T cells expressing at least 2 activation markers: $[Freq^{2+}]$ will be computed as follows:

$$Freq_{Background}^{2+} = \frac{n_{background}^{2+}}{N_{Background}^{CD4}} \quad \text{and} \quad Freq_{Induction}^{2+} = \frac{n_{Induction}^{2+}}{N_{Induction}^{CD4}},$$

And

$$Freq_{Specific}^{2+} = Freq_{Induction}^{2+} - Freq_{Background}^{2+}$$

where

$n_{Background}^{2+}$ = number of CD4+ T cells expressing at least 2 activation markers after stimulation with medium only (background)

$n_{Inductio}^{2+}$ = number of CD4+ T cells expressing at least 2 activation markers after stimulation with a pool of peptides covering RSVPreF3 (induction)

$N_{BackInd}^{CD4}$ = Total number of CD4 T cells involved in the assay (background or induction)

For the computation of the fold increase (post over pre-vaccination) of the frequency of RSVPreF3-specific CD4+ T-cells identified as expressing **at least 2 marker(s)** among IL-2, CD40L, TNF- α , IFN- γ , the results **below the LLOQ** of the assay will be replaced by the value of the LLOQ.

Pre-vaccination will be both pre-Dose 1 in RSV OA=ADJ-002 and pre-Dose 3 in RSV OA=ADJ-011 EXT:002 MTH20. Frequencies will be tabulated by pre-vaccination category according to LLOQ and (Q1-Q3).

- Mean frequencies of RSVPreF3 specific CD4+ T-cells expressing 1 marker, 2 markers, 3 markers or 4 markers among IL-2, CD40L, TNF- α , at Day 1 and Day 31 will be presented graphically
- Median frequencies of RSVPreF3 specific CD4+ T-cells expressing at least 2 will be plotted as a function of time for participants with results available at all time points, considering also the results from study RSV OA=ADJ-002 study.

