5.4. Tertiary endpoints

5.4.1. CMI response up to 1 month post-Dose 3

The following CMI responses will be computed as described in section 5.3.2.1:

- Frequency of RSVPreF3-specific CD8+ T-cells expressing **at least 2 markers** among IL-2, CD40L, TNF- α , IFN- γ , as measured by ICS using PBMCs.
- Frequency of RSVPreF3-specific CD4+ T-cells expressing **at least 2 markers including at least 1 cytokine*** among CD40L, 41BB, IL-2, TNF- α , IFN- γ , IL-13, and IL-17, as measured by ICS using PBMCs.
* *cytokines are IL-2, TNF- α , IFN- γ , IL-13, and IL-17*
- Frequency of RSVPreF3-specific CD4+ T-cells expressing **at least IFN- γ (Th1-like response)**, as measured by ICS using PBMCs.
- Frequency of RSVPreF3-specific CD4+ T-cells expressing **at least IL-13 (Th2-like response)**, as measured by ICS using PBMCs.
- Frequency of RSVPreF3-specific CD4+ T-cells expressing **at least IL-17 (Th17-like response)**, as measured by ICS using PBMCs.
- **Co-expression profile:** Frequency of RSVPreF3-specific CD4+ T-cells expressing **any combination of marker(s) among** CD40L, IL-2, TNF- α , IFN- γ , as measured by ICS using PBMCs, at Day 1 and Day 31 (\rightarrow 15 combinations).

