6. ANALYSIS INTERPRETATION

All analyses are descriptive.

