10.1.4.3. Serological summary statistics

For each assay, geometric mean titers (GMT) or concentrations (GMC) and their confidence limits will be presented with one decimal, as well as GMT/GMC fold increase from pre-dose.

The mean, median, standard deviation and quartile values for frequency of RSVPreF3 specific-CD4+ and CD8+ T cells and for the fold increase (post over pre-vaccination) will be presented with one decimal. The minimum and maximum values will be presented with no decimal.

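### Does the marker-count graph in SAP 5.3.2.1, which has four categories but names three markers and does not say which mean, need to be changed?

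*SAP*

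**What the plan says.** Among the additional considerations for the cell-mediated response, SAP 5.3.2.1 calls for a figure of "Mean frequencies of RSVPreF3 specific CD4+ T-cells expressing 1 marker, 2 markers, 3 markers or 4 markers". The list that completes the sentence has three members: "3 markers or 4 markers among IL-2, CD40L, TNF- α , at Day 1 and Day 31 will be presented graphically". IFN-γ is absent, and the word mean carries no qualifier.

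The same section gives a rule for background-subtracted CD4+ frequencies that are not positive, "by setting to 1 all values less than or equal to zero for geomean calculation and graphical representation". Its fold-increase rule names four markers, IFN-γ among them.

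SAP 5.3.1.2 defines the quantity behind the secondary endpoint as cells "identified as expressing at least 2 activation markers among IL-2, CD40L, TNF- α , IFN- γ". It asks for these to be "summarized by group using descriptive statistics (N, geometric mean, min, Q1, median, Q3, max"), with no arithmetic mean or SD in the list. SAP 5.4.1 plans a co-expression profile of CD40L, IL-2, TNF-α and IFN-γ and puts its size at "15 combinations". The decimals rule in SAP 10.1.4.3 covers "The mean, median, standard deviation and quartile values for frequency of RSVPreF3 specific-CD4+ and CD8+ T cells and for the fold increase" and names no geometric mean for them. SAP section 6 states: "All analyses are descriptive".

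**The concern.** Two things look wrong. First, the number of categories and the list of markers cannot both be right. A programmer who took the list at face value would count marker positivity without IFN-γ. The fourth category would be empty, and many cells would be placed one category too low. The figure would then no longer break down the four-marker endpoint that it is meant to illustrate.

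Second, the SAP never says which mean is drawn, and two of its sections point different ways: 5.3.1.2 lists a geometric mean, while 10.1.4.3 formats a mean with an SD. T-cell frequencies are usually skewed, so the two means can differ a good deal. The choice also decides whether replacing non-positive values by 1 is a necessity (a geometric mean cannot be computed otherwise) or an optional step that can only raise an arithmetic bar. At stake is whether two programmers would draw the same figure, and whether a reader would take the same Day 1 to Day 31 change from it.

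**Working it through.** **Reproducing the SAP's own count.** With k markers there are 2^k − 1 non-empty combinations, of which C(k, j) have exactly j markers.

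| Markers | Exactly 1 | Exactly 2 | Exactly 3 | Exactly 4 | Total |
|---|---|---|---|---|---|
| k = 4 (with IFN-γ) | 4 | 6 | 4 | 1 | 2^4 − 1 = 15 |
| k = 3 (as listed) | 3 | 3 | 1 | 0 | 2^3 − 1 = 7 |

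The 15 in SAP 5.4.1 is reproduced only with four markers.

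**What a literal reading would do.** IFN-γ is in 2^3 = 8 of the 15 combinations. Without it, 1 moves from four markers to three, 3 from three to two, 3 from two to one, and 1 from one to none. Of the 6 + 4 + 1 = 11 combinations that count toward the endpoint, the 3 made of IFN-γ and one other marker drop below two.

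**Whether the text allows that reading.** The figure needs a four-marker category. The endpoint tables (Protocol Table 3, SAP section 2), the summaries in SAP 5.3.1.2, the fold-increase rule in 5.3.2.1 and the profile in 5.4.1 all use the same set for CD4+ cells: IL-2, CD40L, TNF-α and IFN-γ. Nowhere is a three-marker CD4+ set defined. The list in the figure bullet ends in a comma where the fourth name would stand, and the next bullet, on median frequencies, also lacks its noun after the number 2. This is careless drafting, not a different analysis. The SAP of 1 December 2020 has the same sentence, so it is not an artefact of text extraction.

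**Which mean.** Where the SAP intends a geometric statistic it says so: geometric mean in 5.3.1.2, the geomean in 5.3.2.1, and GMT or GMC in 5.2.1.2 and 10.1.3.4. Where it writes mean alone, it is for ordinary descriptive statistics: age in 5.1.1, days with solicited events in 5.2.2.1.1, and baseline characteristics in 10.1.4.2. By that usage the figure shows arithmetic means. Section 10.1.4.3 belongs to the rules on display of decimals; it formats statistics that may be shown and does not compete with 5.3.1.2, which repeats the list in Protocol 9.4.4.2.

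**How far the means could differ.** The documents give no frequencies or SDs, so this part is assumed. For lognormal data with log10 SD s, the ratio of arithmetic to geometric mean is exp[(s × ln 10)² / 2]:

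- s = 0.3: exp(0.6908² / 2) = 1.27
- s = 0.4: 1.53
- s = 0.5: 1.94
- s = 0.6: exp(1.3816² / 2) = 2.60

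Suppose instead that a share f of values is set to 1 and the rest equal 100 per million. The arithmetic mean is f + 100(1 − f) and the geometric mean is 100^(1 − f). For f = 0.1 these are 90.1 and 63.1; for f = 0.3 they are 70.3 and 25.1. The gap is real under either assumption, but it is a general property of skewed data.

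**The value of 1 in graphs.** The rule in 5.3.2.1 covers graphical representation as well as the geometric mean, and this is a graph. It applies whichever mean is drawn, so nothing is left undecided.

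**The case for a change.** The strongest case for acting is that a SAP should lead two programmers to the same output, and here three figures could be defended: geometric means with non-positive values set to 1, arithmetic means with the same substitution, or arithmetic means of the raw differences. Only the last, over four markers, makes the bars for two, three and four markers add exactly to the arithmetic mean of the endpoint. Simulated examples with 100 pairs and eight assumed set-ups give a sense of the spread. For true Day 31/Day 1 ratios of 2 to 4, the four-marker bar showed 2.0 to 4.0 with unsubstituted arithmetic means and 2.1 to 5.6 with geometric means. Substitution raised the Day 1 arithmetic bar for four markers by 0% to 25%. A few words would settle the matter.

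Part of this stands. The missing marker is an error, and the kind of mean is not stated in so many words. The rest carries less weight.

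- The documents nowhere ask the bars to add to the endpoint, and the arithmetic mean they would add to is not in the list in 5.3.1.2.
- Plotting raw differences would set aside a stated rule for graphs and could give negative bars.
- Every frequency, SD and noise level in the simulation is invented. The largest substitution effects come from set-ups where the noise SD (50 per million) exceeds the assumed four-marker median (0.10 × 300 = 30 per million). With a noise SD of 25 the effect was about 2% or less.
- Arithmetic means with substitution, the plainest reading of the text, gave ratios of 3.2 to 4.0 where the truth was 4, about 3.0 where it was 3, and 2.0 where it was 2. That reading did not overstate the change.

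**Conclusion.** This is a clerical slip that the SAP itself resolves, together with a detail that its own usage fills. IFN-γ belongs in the list: the four-marker category, the definitions in the neighbouring sections and the count of 15 all require it. Unqualified means are arithmetic by the SAP's convention, and the handling of non-positive values in graphs is already fixed. The conclusion on the marker set rests on counting alone. The conclusion on the mean rests on how the SAP uses the word elsewhere and is somewhat less certain.

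If an analyst chose the geometric mean instead, bar heights could differ by a factor of roughly 1.3 to 2.6 under the assumed log10 SDs of 0.3 to 0.6, and a label on the axis would tell the reader which was used. The consequence stops at one supplementary figure. The co-expression profile in SAP 5.4.1 reports all 15 combinations at Day 1 and Day 31, so the breakdown by number of markers can be recovered from the same data. The protocol has no hypotheses (9.1) and no sample size calculation (9.2). No tabulated median, fold increase, endpoint or conclusion moves, so no change to the plan is called for.
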